#### RPV LA

The RPV PK acceptable criteria following LA administration is:

• A median Wk. 12 (Cohort 1) or Wk. 8 (Cohort 2b) Ct between 25-100 ng/mL

The study team will review all of the PK parameters following oral and long-acting CAB and RPV, safety and tolerability/acceptability data to determine if dose modifications are warranted (for each drug, for each formulation and for each weight band).

#### Potential Dose Modification

Dose adjustments for management of individual participant PK target exposures will not occur. In the event of failure with respect to safety and/or PK criteria that are deemed potentially avoidable by lower (or higher) exposure to the study drugs, as judged by the CMC, a dose adjustment will be considered for the applicable weight band. As noted in Section 5.1.2, dosing regimen modifications for each weight band may occur as needed following the Cohort 1 interim analyses and/or based on ongoing reviews of safety, PK, and all other relevant data, and will be implemented across all participants within the applicable weight band group. During the reviews of the data and based on the findings, the protocol team may decide whether to continue with Q4W dosing, move to Q8W dosing, change to a different dose on either the Q4W or Q8W schedule, or gather additional data on the initial Q4W dosing regimen for each weight band.

At the two planned interim analyses, and at any other additional relevant PK analysis, the PK parameters calculated from each individual participant will be used to predict that participant's exposure at Wk. 12 (Cohort 1) or Wk. 8 (Cohort 2b) if they were taking Q8W injections instead of Q4W (via modeling and simulation). Using the *predicted* Q8W dose interval trough concentrations from each participant, the same trough acceptance criteria will be applied as already noted in the protocol above. The same strategy will be used, if needed, during ongoing study PK analyses to assess alternate doses or dose intervals if particular weight-bands do not meet acceptance criteria for either the oral or the LA dosing. In other words, based on the observed PK data from each participant, those participants' predicted exposures on the new dose or dose regimen will be calculated, and the acceptance criteria will be applied to those individual participants' predictions on that new dose or dose interval.

When assessing whether to change the dose interval, if the median of the predicted concentrations from every 8 week dosing meets the LA dosing trough acceptance criteria, new participants in the corresponding Weight Bands may be initiated on every 8 week dosing. Ongoing study participants that enrolled on every 4 week dosing may also transition to every 8 week dosing after their week 24 visit.

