#### 6.1.2 Additional Considerations for a Q8W Injection Schedule

In the event of a dosing regimen modification (see Section 5.1.2), the follow-up visit schedule for each cohort will remain per Sections 6.3 through 6.6 and per Appendix I. However, injections and other select visit procedures, as specified below, will only occur at a Q8W frequency.

Participants newly enrolling into the study on a Q8W injection schedule will have injectable study product administered at the following visits:

- For Cohort 1 (through Week 72) and Cohort 2a (through Week 48 only): Weeks 4b, 8, 16, 24, 32, 40, 48, 56, 64, and 72.
- For Cohort 2b: Entry, Week 4, and at Weeks 12, 20, 28, 36, 44.

When receiving injectable study products on a Q8W schedule, acceptability/tolerability assessments for participants and parents/caregivers and all laboratory evaluations (including urine pregnancy tests and all bloodwork) will be administered on a Q8W schedule and will only take place at injection visits. Non-injection visits for participants on a Q8W injection schedule may be conducted in person or telephonically.

See the IMPAACT 2036 MOP for further details regarding implementation of a dosing regimen modification and associated procedural changes when moving from Q4W to Q8W dosing.

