#### CAB LA

The CAB PK acceptable criteria following LA administration is:

• A median Wk. 12 (Cohort 1) or Wk. 8 (Cohort 2b) trough (prior to next LA dose; Ct) concentration between 0.71-6.7 mcg/mL

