# **Injectable Dosing:**

**Table III: Injection Interval** 

III.A	Q. 4 weeks
III.B	Doses 1 and 2, 4 weeks apart, then Q. 8 weeks

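### The every-8-week (Q8W) trough test is tied to Week 12 (Cohort 2b: Week 8), which is the middle of the Q8W interval, so the rule contradicts itself and the Q8W schedule

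*Protocol*

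**What the plan says.** Section 10.3.1 sets the limits for the long-acting injections. For CAB LA it requires "A median Wk. 12 (Cohort 1) or Wk. 8 (Cohort 2b) trough (prior to next LA dose") of 0.71 to 6.7 mcg/mL. For RPV LA, at the same weeks, the median must lie "between 25-100 ng/mL".

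Under Potential Dose Modification, each participant's PK parameters are used to predict that child's "exposure at Wk. 12 (Cohort 1) or Wk. 8 (Cohort 2b) if they were taking Q8W injections instead of Q4W". The next sentence turns to troughs forecast under 8-weekly dosing: "dose interval trough concentrations from each participant, the same trough acceptance criteria will be applied as already noted in the protocol above". A later paragraph, on changing the interval, names no week: Q8W may be started "if the median of the predicted concentrations from every 8 week dosing meets the LA dosing trough acceptance criteria".

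The Q8W schedule is set elsewhere. Section 6.1.2 gives injections at "Weeks 4b, 8, 16, 24, 32, 40, 48, 56, 64, and 72" for Cohorts 1 and 2a, and at "Entry, Week 4, and at Weeks 12, 20, 28, 36, 44" for Cohort 2b. Appendix VII Table III describes the interval as "Doses 1 and 2, 4 weeks apart, then Q. 8 weeks".

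**The concern.** A trough is the concentration just before the next dose, and the CAB criterion says so. Under Q4W, Week 12 in Cohort 1 (Week 8 in Cohort 2b) is such a point. Under Q8W no injection is due then. Section 10.3.1 therefore fixes the Q8W evaluation at a week that is not a trough, while calling the quantity a trough.

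This matters because it is the stated PK rule for the dosing interval. Meeting it allows new participants to start on Q8W and ongoing ones to move after Week 24. Under Section 5.1.2, children still in the oral lead-in when the regimen changes also go to Q8W. Section 1.2.5.1 warns that sub-therapeutic concentrations could lead to virologic failure and possibly resistance. Two analysts following the same text could test different time points, and near the lower limits they could reach different answers.

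**Working it through.** The plan gives no figure to reproduce here, so the check is a calendar comparison followed by an illustration of size.

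**Inputs**
- Injection weeks under Q8W: Section 6.1.2 and Appendix VII Table III.
- Visit days: Appendix II. Counting from Week 4b, Week 8 is day 28, Week 12 is day 56 and Week 16 is day 84. In Cohort 2b, counting from Entry, Week 4 is day 28, Week 8 is day 56 and Week 12 is day 84.
- Lower limits: CAB 0.71 mcg/mL and RPV 25 ng/mL (Section 10.3.1).
- RPV LA apparent half-life in adults: 200 days (Section 1.2.2).
- CAB LA half-life: not given. Assumed range 28 to 112 days (4 to 16 weeks).

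**Step 1. Days since the last injection**

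| Visit | Q4W | Q8W |
|---|---|---|
| Cohort 1, Week 12 (day 56) | 56 − 28 = 28 | 56 − 28 = 28 |
| Cohort 1, Week 16 (day 84) | 84 − 56 = 28 | 84 − 28 = 56 |
| Cohort 2b, Week 8 (day 56) | 56 − 28 = 28 | 56 − 28 = 28 |
| Cohort 2b, Week 12 (day 84) | 84 − 56 = 28 | 84 − 28 = 56 |

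Under Q8W the named week is exactly halfway through the 56-day interval. The first visit that ends a Q8W interval is Week 16 (Cohort 2b: Week 12).

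**Step 2. What a prediction at the named week can show**

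Before day 56 both schedules contain the same injections, on days 0 and 28. With unchanged doses, any model gives the same concentration at day 56 for both intervals. The predicted Q8W value then equals the Q4W value and meets the limits exactly when the Q4W value does. If the doses are changed too, the values differ, but the point is still mid-interval.

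**Step 3. Illustrative size**

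Under Q8W no dose is given between day 56 and day 84. If the decline is mono-exponential over that period, the ratio does not depend on the dose:

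C(Week 16) / C(Week 12) = 2^(−28 / half-life in days)

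The Week 12 value needed for Week 16 to reach the limit is the limit divided by this ratio. The same arithmetic holds for Weeks 8 and 12 in Cohort 2b.

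| Drug | Half-life (days) | Ratio | Week 12 value needed |
|---|---|---|---|
| RPV | 200 (stated) | 2^(−0.14) = 0.908 | 25 / 0.908 = 27.5 ng/mL |
| CAB | 28 (assumed) | 2^(−1) = 0.500 | 0.71 / 0.500 = 1.42 mcg/mL |
| CAB | 56 (assumed) | 2^(−0.5) = 0.707 | 0.71 / 0.707 = 1.00 mcg/mL |
| CAB | 84 (assumed) | 2^(−0.333) = 0.794 | 0.71 / 0.794 = 0.89 mcg/mL |
| CAB | 112 (assumed) | 2^(−0.25) = 0.841 | 0.71 / 0.841 = 0.84 mcg/mL |

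A Week 12 median between the limit and the value in the last column would pass at Week 12 and fall short at Week 16.

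**Step 4. Comparison with the rest of the protocol**

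Table 12 (Section 10.4) works with troughs at Week 24, or Week 20 without the lead-in. Both are end-of-interval visits under Q8W. Section 10.3 schedules pre-injection samples at Week 16 (Cohorts 1 and 2a, both sampling schedules) and Week 12 (Cohort 2b), but no Week 8 PK sample in Cohort 2b. Section 6.1.2 also confines bloodwork on Q8W to injection visits, so a child on Q8W in Cohort 1 would have no Week 12 sample.

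**The case against.** A reader might infer that the test cannot show at all whether Q8W troughs are adequate. The documents do not support that. The sentence that applies the limits refers to predicted Q8W dose-interval troughs, the interval-change paragraph names no week, and a model can produce a Week 16 prediction. An analyst who follows the word trough would do the right thing. But that analyst must override the only week stated, both in the prediction sentence and in the criteria it points back to.

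A reader might also infer that Q8W passes whenever Q4W passes. That holds only at unchanged doses and on the literal reading. Section 10.3.1 allows a different dose on either schedule, and Appendix VII selects dose and interval separately.

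Nor does it follow that children will be moved to Q8W with inadequate troughs. Meeting the criterion permits a switch and does not compel one. The Clinical Management Committee reviews PK, safety, viral load and tolerability together, and Section 9.5.4 requires Study Monitoring Committee review before any move to Q8W. Pre-injection samples and viral loads continue afterwards. These safeguards are real, but both committees would be looking at the misaligned prediction.

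The band at risk may also be narrow. The adolescent Week 16 CAB median in Section 1.2.4 is 3.11 mcg/mL; even multiplied by the lowest ratio above, 3.11 × 0.50 = 1.56, which exceeds 0.71. The adult Q8W geometric means under Table 12 (1.6 mcg/mL CAB, 57.16 ng/mL RPV) also lie within the limits. Those are other populations, so they reassure without settling the matter.

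Finally, Section 10.5 defers PK detail to a PK analysis plan and a modelling plan that are not shown. They may name the right week, but the protocol's own text would still conflict.

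**Conclusion.** The point stands as an internal contradiction. Section 10.3.1 names Week 12 (Cohort 2b: Week 8) and calls the Q8W value there a trough. Section 6.1.2 and Appendices II and VII place that week 28 days into a 56-day interval. This rests on the calendar alone.

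The size rests on mono-exponential decline from Week 12 to Week 16. For RPV, carrying over the stated adult half-life, the Week 12 value overstates the trough by about 10% (1 / 0.908), and only medians from 25 to about 27.5 ng/mL would be affected. For CAB the size is unknown from the documents. Assuming 4 to 16 weeks, the ratio is 0.50 to 0.84, and the affected medians run from 0.71 up to between 0.84 and 1.42 mcg/mL. Nothing in the documents shows that a weight band will fall there.

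This should be fixed. It could change an interim conclusion near the lower limit and is cheap to correct, but it does not show that the interval decision is invalid.

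**What to change.** Reconcile the PK acceptance criteria and Potential Dose Modification text in Section 10.3.1 with Section 6.1.2 and Appendices II and VII. State that, for any Q8W prediction or observation, the evaluation time point is the pre-injection sample at the end of the 8-week interval: first at Week 16 in Cohorts 1 and 2a, and at Week 12 in Cohort 2b. Keep Week 12 and Week 8 for Q4W only. Have the interval-change paragraph name the same time point, and carry it into the PK analysis plan. The acceptance limits, the doses and the choice of interval remain with the sponsor.

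The cost is a few sentences. The simulation is already planned and the samples are already scheduled, so no visit or blood draw is added. The downside is that Q8W may meet the criterion less often.

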#### 10.4 Pharmacokinetic Sample Size Justification

See Section 3 and Section 9.4 for details regarding the sample size and accrual targets for the study, including stratification requirements. The total sample size for Cohort 1 and 2 was primarily driven by safety outcome measures, but the total number of participants, including the minimum of 6 participants required in each Weight Band in Cohort 1, and a minimum of 4 participants in each Cohort 2a and 2b are sufficient to characterize the PK profile based on the statistical precision.

The precision was estimated using PK trough concentration for the sample sizes of the minimum of 4 (Cohort 2a and Cohort 2b) and 6 (each weight band in Cohort 1), respectively, as shown in Table 12 For example, with a minimum of 4 participants in Cohort 2a or 2b, the precision can be achieved with 90% CI of sample geometric mean trough concentration ( $C_t$  prior to IM doses) at Week 20/24 being 0.84 -3.06 ug/mL for CAB, and 32.11-101.74 ng/mL for RPV. Therefore, the predicted 90% CI will allow to exclude a value of 4 X PA-IC90 (0.664 ug/mL) for CAB, and rule out a value of 2 X PA-IC90 (24 ng/mL) for RPV.

Table 12.

Statistical Precision When Estimating PK Trough Concentration at Week 20 (direct to injection)/ Week
24 injection visit (oral lead-in followed by LA)

	N		Assumpt	tion	Precision + when	
Study drugs		Mean (LgConc.)	SD (LgConc.)	Geo. Mean*	estimating trough Concentration 90%CI	
			Assumption 1: Pl	K Trough data from A	ΓLAS-2M	
CAB (ug/mL)	6	0.47	0.55	1.6	1.02	2.52
	4	0.47	0.55	0.55		3.06
RPV (ng/mL)	6	4.05	0.40	77 4 6	38.20	85.54
	4	4.05	0.49	57.16	32.11	101.74
		Assur	nption 2: 10% incre	ase of SD (LgConc.) f	rom Assumption 1	
CAB (ug/mL)	6	0.47	0.61	1.6	0.97	2.63
	4	0.47	0.01	1.6	0.79	3.26
RPV (ng/mL)	6	4.05	0.54	57.16	36.69	89.06
	4	4.03	0.54	37.10	30.31	107.78

		Assum	ption 3: 30% increa	ase of SD (LgConc.) fr	om Assumption 1	
CAB (ug/mL)	6	0.47	0.72	1.6	0.89	2.88
	4	0.47	0.72	1.6	0.69	3.71
RPV (ng/mL)	6	4.05	0.64	57.16	33.85	96.53
	4	4.03	0.04	37.10	27.01	120.95
		Assum	ption 4: 50% increa	ase of SD (LgConc.) fr	om Assumption 1	
CAB (ug/mL)	6	0.47	0.93	1.6	0.81	3.15
	4	0.47	0.83	1.6	0.61	4.22
RPV (ng/mL)	6	4.05	0.74	57.16	31.22	104.64
	4	4.03	0.74	37.10	24.07	135.74

+Precisions were calculated based on t-distribution.

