Once enrolled into Cohort 1, participants in each weight band will move through two steps of study participation. In Step 1 (i.e., at study entry), participants will switch from their pre-study ART regimen to daily oral formulations of CAB + RPV for at least four weeks and up to a maximum of six weeks. Participants who meet the eligibility criteria outlined in Section 4.3 and Section 4.4 based on Week 4a visit will transition to Step 2 and receive injectable CAB LA + RPV LA through Week 72. Additional information about transitioning from Step 1 to Step 2 is provided in Section 3.3. Participants who prematurely and permanently discontinue oral CAB + RPV or do not meet eligibility criteria for the injection phase will exit the study 28 days after their last oral study product dosing (See Section 6.3.3). In Step 2, participants will receive injectable CAB LA + RPV LA. Two IM injections, a single injection of CAB LA and a single injection of RPV LA, will be administered at the Week 4b (Step 2 Entry) visit, at the Week 8 visit, and then continuing every four weeks or every eight weeks thereafter, depending on the recommendation of the Week 12 interim analyses (See Section 3.2), with the last injections administered at the Week 72 visit. In both steps, participants will follow the dosing regimens outlined in Section 5.1.

Once Cohort 1 has completed accrual (defined as having enrolled either 50 evaluable participants, as described in Section 3.2, or a maximum of 70 participants overall) and the results of both interim analyses are available and acceptable, Cohort 2 will open to accrual. Cohort 2 will have a planned accrual period of six months, during which up to 20-40 children may enroll (across both Cohort 2a and Cohort 2b, described below). Participants may enroll into either Cohort 2a or 2b, with a minimum accrual target of 4 participants in each. While distribution across weight bands is desirable, there are no weight band requirements for Cohort 2. Should the overall study sample size maximum (approximately 90 children enrolled across all cohorts) not be reached within the sixmonth accrual period for Cohort 2, then Cohort 2 will close to accrual either when the six-month accrual period is completed, or upon reaching the minimum accrual target, whichever is later.

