The analysis for the Primary Analysis Report will be performed when Cohort 1 complete data through Week 24 are available. Additional analysis reports for supporting regulatory submissions or publication (e.g., safety update, HTA-health technology assessment) and final reports which include data beyond Week 24 will be generated. The details of analyses for these reports will be specified in the Primary Statistical Analysis Plan (Primary SAP) and other study analysis planning documents.

The study is designed to allow changing the dose regimen as described in Section 5.1.2. The study also allows for the use of oral bridging during the injection phase. Analysis specifications related to any dose changes or the use of oral bridging are in Section 9.6. Additional specifications may be added in the Primary SAP.

Participants assigned or who opt to receive LA injectable regimen with oral lead-in of CAB and RPV, i.e., participants in Cohort 1 and 2a, may fail the Step 2 eligibility criteria and thus are not able to proceed with the injectable phase of the regimen. The Primary SAP will describe the analyses to address the safety objectives in case some Cohort 1 and 2a participants do not proceed with the injectable phase of the regimen.

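### Section 10.4's Cohort 2 precision needs 4 observed Week 24/20 troughs, but the minimum of 4 per group counts enrolled children; with one trough missing, the CAB interval no longer excludes 0.664 ug/mL

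*Protocol*

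**What the plan says.** Section 10.4 treats the minimum group sizes, including 4 children in each of Cohorts 2a and 2b, as enough to describe the PK profile. Its worked example is that "with a minimum of 4 participants in Cohort 2a or 2b, the precision can be achieved", "with 90% CI of sample geometric mean trough concentration" at Week 20/24 of 0.84-3.06 ug/mL for CAB and 32.11-101.74 ng/mL for RPV. It concludes: "Therefore, the predicted 90% CI will allow to exclude a value of 4 X PA-IC90 (0.664 ug/mL) for CAB", and likewise that 24 ng/mL is ruled out for RPV. Table 12 repeats the calculation with the SD raised by 10%, 30% and 50%.

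The Schema and section 3.1 set the same number at enrolment: children join 2a or 2b "with a minimum accrual target of 4 participants in each". Section 3.2 defines evaluable participants for Cohort 1 only. Section 9.1 foresees that children in Cohorts 1 and 2a "may fail the Step 2 eligibility criteria and thus are not able to proceed with the injectable phase of the regimen". Section 8.6 says that withdrawn participants are not replaced.

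**The concern.** The precision calculation and the accrual rule use the same number for different things. The calculation needs 4 measured troughs some 20 weeks into injections. The accrual rule secures 4 children at entry.

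A Cohort 2a child who fails Step 2 leaves the study after an Early Termination visit (sections 6.3.3 and 8.5) and never has an injection trough. In either group, a child who stops before Week 24 or Week 20, or misses the pre-dose sample, also contributes nothing to this estimate. Section 10.4 makes no allowance for any of these.

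The floor can be reached. Under section 3.1, if the overall maximum is not met, Cohort 2 closes at six months or when the minimum is reached, whichever is later. Families choose the group, so the split may be uneven. At stake is whether the design, at its own minimum size, delivers the precision claimed for that size.

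**Working it through.** **Inputs, all from section 10.4 and Table 12 (Assumption 1).**
- CAB: log SD 0.55, geometric mean 1.6 ug/mL (table row "CAB (ug/mL) 6 0.47 0.55 1.6 1.02 2.52").
- RPV: log SD 0.49, geometric mean 57.16 ng/mL (table row "4 4.05 0.49 57.16 32.11 101.74").
- Method: "Precisions were calculated based on t-distribution", two-sided 90%.
- Values to exclude: 0.664 ug/mL (CAB) and 24 ng/mL (RPV).

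**Formula.** GM x exp(± t(0.95, n-1) x SD/√n). This is the interval when the sample mean and SD equal the assumed values, as in Table 12.

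**The protocol's own figures, n=4, t(0.95, 3) = 2.353.**
- CAB: 1.6 x exp(± 2.353 x 0.55/2) = 0.84-3.06.
- RPV: 57.16 x exp(± 2.353 x 0.49/2) = 32.11-101.74.

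Both match section 10.4. The n=6 rows also reproduce (CAB 1.02-2.52; RPV 38.20-85.54).

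**One trough missing, n=3, t(0.95, 2) = 2.920.**
- CAB: 1.6 x exp(± 2.920 x 0.55/√3) = 0.63-4.04. The lower limit, 0.633, is below 0.664.
- RPV: 57.16 x exp(± 2.920 x 0.49/√3) = 25.0-130.6. The lower limit is just above 24. With the SD raised by 10% (0.539) it is 23.0 and the exclusion is lost.

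**Five troughs.** The CAB interval is 0.95-2.70, so the exclusion holds with room to spare.

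**Largest log SD at which the CAB lower limit stays above 0.664.** SD = √n x ln(1.6/0.664)/t.
- n=4: 2 x 0.8795/2.353 = 0.747, which is about 36% above 0.55 (0.747/0.55 = 1.36).
- n=3: 1.732 x 0.8795/2.920 = 0.522, which is below the assumed 0.55.

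This agrees with Table 12 at n=4: the CAB lower limit is 0.69 in the +30% row and 0.61 in the +50% row.

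**Chance of at least one missing trough among 4.** The protocol gives no loss rate for Cohort 2, so a per-child rate p is assumed: 1-(1-p)^4.
- p = 0.05: 1-0.95^4 = 0.185, or 19%.
- p = 0.10: 1-0.90^4 = 0.344, or 34%.

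**The case against.** No printed figure is wrong: every interval in section 10.4 follows from its stated inputs. What is missing is the condition that all 4 children contribute a trough.

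The problem also needs two things together, a group that ends at or near 4 and a loss within it. Cohort 2 is planned for up to 20-40 children, and 5 observed troughs already restore the CAB exclusion. Step 2 failure cannot occur in 2b.

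Little depends on the claim. Cohort 2 PK is a secondary objective to describe (section 2.3.2), and section 10.4 says that total sample size was driven mainly by safety. The long-acting PK acceptance criteria in section 10.3.1 use median troughs at Week 12 (Cohort 1) or Week 8 (Cohort 2b), not this interval. The CAB shortfall at n=3 is 0.633 against 0.664, about 5%. All of this stands and limits the weight of the point. It does not remove the mismatch between enrolled children and observed troughs.

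Two stronger readings are tempting, and the document does not support them. First, a reader might infer that Table 12's +50% row (CAB lower limit 0.61 at n=4) conflicts with the prose. The prose is offered as an example on the base case, and the table openly shows the larger SDs as sensitivity results. The prose could carry the SD condition, but nothing conflicts. Second, a reader might take the Cohort 1 figures, up to 70 enrolled for at least 50 evaluable, as a planned loss of 20/70 and apply it here. Seventy is an enrolment ceiling. Evaluable in section 3.2 also does not mean having a Week 24 trough: a child who stops early with a qualifying drug-related event is evaluable without one.

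**Conclusion.** The point holds and is minor. Section 10.4 states a precision that the design does not secure at its own minimum, because 4 enrolled children need not give 4 troughs. With one missing, the CAB exclusion of 0.664 ug/mL is lost under the protocol's base-case SD, while RPV still just excludes 24 ng/mL.

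This rests on Table 12's adult-derived geometric means and SDs, and on a group finishing at the floor. The 19-34% chance of a missing trough depends on the assumed 5-10% loss per child and is an illustration, not a protocol figure. No dosing decision is tied to this interval.

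**What to change.** In section 10.4:
- State that the Cohort 2 precision applies with 4 children contributing a Week 24 (2a) or Week 20 (2b) pre-dose trough.
- Add an n=3 row under Assumption 1: CAB 0.63-4.04 ug/mL; RPV 25.0-130.6 ng/mL.
- Add that at n=4 the exclusion of 0.664 ug/mL for CAB holds for a log SD up to about 0.75 (about 36% above 0.55), and so not in Table 12's +50% row.

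This needs no extra children and no design change. The cost is a slightly less favourable stated precision.
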